5.3. Criteria for the exclusion of subjects

1. Withdrawal of informed consent by the patient and/or the patient's legal representative.
2. Need for additional therapy not permitted under this protocol.
3. Serious adverse events or adverse events that do not fulfil the criteria for seriousness and where, in the opinion of the investigator, further participation in the trial would be dangerous to the health or well-being of the patient.
4. Investigator or sponsor's decision to exclude a patient due to a significant protocol deviation/protocol violation.
5. Any patient condition that, in the reasonable judgement of the investigator, requires the

patient to be withdrawn from the trial.

6. Positive result of at least one of the following tests: blood tests for HIV, syphilis, hepatitis B and C, if the test results are obtained after the patient's randomization procedure.
7. Allergic reaction to trial medications requiring their cancellation.
8. Loss of contact with the patient followed by failure to attend the visit.
9. Recurrent stroke.
10. Positive result of the rapid test for IgM antibodies to SARS-CoV-2 virus and/or positive result of laboratory examination for the presence of SARS-CoV-2 RNA using nucleic acid amplification methods, regardless of clinical manifestations.
11. Diseases and/or conditions of the subject detected for the first time during routine medical examinations and procedures that prevent the subject from continuing his/her participation in the trial, and/or indicate that the patient was wrongly included in the trial (failure to meet the selection criteria for the trial at the time of inclusion).

5.4. Termination of subjects' participation in the trial

5.4.1. Procedures for excluding subjects from the trial

Criteria for non-inclusion of patients in the trial (assessed at the screening stage) are presented in section 5.2.

The criteria for exclusion of patients from the trial (assessed throughout the trial in accordance with the description of the trial procedures and the Schedule of Trial Procedures (Appendix 1) are presented in Section 5.3.

If a patient decided to withdraw from the trial or did not complete the trial for any reason, his/her randomization code should not be reused.

Patients who were excluded from the trial during screening prior to the administration of investigational therapy should not be randomized into this trial.

Excluded subjects will be monitored for the development of AE/SAE until their resolution or stabilisation of AE/SAE-induced manifestations.

5.4.2. Data collection by type and timing for subjects who discontinued participation in the trial

The investigator transmits data on patients excluded from the trial to the Sponsor and the Clinical Research Associate within 24 hours in the form of a report that includes information about the patient's status at the end of the trial.

Patient status at the end of the trial:

1. Finished the trial.
2. Did not finish/discontinued because of:
 - trial error;
 - adverse events;
 - serious adverse events;
 - pregnancy;
 - protocol violations;
 - patient's desire to withdraw from the trial;
 - due to a patient's failure to appear;
 - other reasons (specify).

5.4.3. Substitution of trial participants

This trial does not provide for the replacement of withdrawn trial participants.

5.4.4. Follow-up of excluded subjects

If no dose of the investigational product/comparator product was received by the patient and the patient withdrew from the trial for any reason, he/she is not followed up further and

his/her data are not included in the statistical analysis.

If the investigational product/comparator product was received by the patient and the patient is withdrawn from the trial for any reason unrelated to the development of an AE, including failure to attend the next visit for an unknown reason, the investigator should contact the patient and schedule a date for the patient's end-of-trial visit.

If SAEs occur, the patient should be monitored by a physician according to the AE surveillance guidelines.

Follow-up of excluded patients due to the development of AE/SAE will be carried out until resolution or stabilization of AE/SAE-induced manifestations.

6. Trial design

6.1. Schedule of trial visits and procedures

As part of this trial, the patient will participate in the following clinical trial periods:

- **Screening (Visit 0)** - pre-screening of patients. The duration of the period should not be more than 24 hours from the time of the informed consent procedure to randomization. Screening, randomization and initiation of therapy can be done on the same day.
- **Randomization and initiation of therapy** (Visit 1) - randomization of patients, initiation of trial therapy.
- **Therapy period** (70 days in total), use of investigational product/placebo (10 days - parenteral administration period, 60 days - oral administration), patient assessment, registration of AEs.

Patients will be assessed at the following visits.

Screening:

Visit 0 (Day -1 / Day 1¹) - screening, preliminary examination of patients, initiation of therapy.

Visit 0 procedures should be carried out within a maximum of 24 hours and may be carried out on the same day as Visit 1 procedures:

- Signing an informed consent form;
- Collection of demographic and anthropometric data, anamnesis;
- Physical examination
- Neurological examination;
- Assessment of vital signs (BP, HR, RR, body temperature);
- Clinical blood test;
- Blood chemistry;
- Blood tests for HIV, syphilis, hepatitis B and C²
- SARS-CoV-2 IgM antibody rapid test
- Urinalysis;
- Pregnancy test for women with preserved reproductive potential;
- ECG³;
- Completion of specialized scales (mRS, NIHSS);
- CT/MRI³;
- Assessment of prior and concomitant therapy;
- Assessment of inclusion/non-inclusion criteria

¹ Visit 0 - patient screening - is conducted on Day 1 if Visit 0 and Visit 1 are conducted on the same day.

² Results obtained within 48 hours prior to Screening may be used.

³ If data are available for a patient from instrumental examinations performed within 48 hours prior to inclusion in the trial, they can be used to assess the patient's condition and eligibility for inclusion/non-inclusion. The use of such data shall be permitted only if the data are available in full and for all parameters required by the Protocol.

Randomization and initiation of therapy

Visit 1 (Day 1)

- Randomization
- Completion of specialised scales and calculation of indices (HADS, MoCA, Rivermead mobility index);
- Prescribing and initiation of investigational therapy;
- AE registration

Therapy period:

Includes standard therapy prescribed to the patient depending on the clinical picture of the disease and symptomatology.

The investigational therapy is assigned to the patient according to the results of the randomization procedure.

Visit 2 (day 11/12¹ from the start of therapy, Visit procedures are performed at the end of parenteral therapy):

Physical examination, neurological examination, assessment of vital signs (BP, HR, RR, body temperature), assessment of concomitant therapy, registration of AE and assessment of exclusion criteria, clinical and biochemical blood tests, urinalysis, ECG, completion of specialised scales and calculation of indices (mRS, NIHSS, HADS, MoCA, Rivermead mobility index), dispensing of oral medication.

Telephone call 1 (Day 24±2 from initiation of therapy; Day 14±2 from initiation of oral therapy): assessment of concomitant therapy, recording of AE and assessment of exclusion criteria, assessment of compliance.

Visit 3 (Day 40 (+2) from initiation of therapy; Day 30 (+2) from initiation of oral therapy): physical examination, assessment of vital signs (BP, HR, RR, body temperature), assessment of concomitant therapy, recording of AE and assessment of exclusion criteria, dispensing/administration of oral medication, assessment of compliance.

Telephone call 2 (Day 55±2 from initiation of therapy; Day 45±2 from initiation of oral therapy): assessment of concomitant therapy, recording of AE and assessment of exclusion criteria, and assessment of compliance.

Visit 4 (day 71(+2) from the start of therapy; end of therapy): physical examination, neurological examination, assessment of vital signs (BP, HR, RR, body temperature), assessment of concomitant therapy, registration of AE and assessment of exclusion criteria, clinical and biochemical blood tests, general urinalysis, pregnancy test for women with preserved reproductive potential, ECG, completion of specialised scales and calculation of indices (mRS, NIHSS, HADS, MoCA, Rivermead mobility index), return of the IP and assessment of compliance.

Additional in-person/out-person (phone calls) visits may be conducted if necessary, in the reasonable judgement of the investigator, particularly to monitor the progression of SAEs. The scope of activities and procedures performed at additional visits will be determined by the investigator on an individual basis, depending on the indications.

In case of early withdrawal of a patient from the trial, a Visit to End Patient Participation in the Trial is performed, including activities identical to those of Visit 4.

The schedule of the trial procedures is presented in *Appendix 1*.

¹ If the first administration of the investigational product (start of parenteral therapy) falls on the second half of the day (the first day of therapy - one administration of the trial drug), Visit 2 is performed on day 12 in the morning.

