If a patient develops an AE, the investigator should enter the necessary information into the CRF by completing the appropriate pages and assess whether the patient can continue to participate in the trial (continue the IP or exclude the patient from the trial). If a SAE develops, the investigator completes the SAE registration form provided by the Sponsor/contract research organisation representative, assesses whether it is associated with the investigational product and faxes the completed form to the Sponsor/contract research organisation representative. The original SAE form and fax receipt acknowledgement sheet should be retained in the source documentation, and the information should be entered into the patient's CRF. SAEs are reported to the LEC; SAEs deemed to be SUARs are reported to regulatory authorities, in accordance

with pharmacovigilance practices. The CRO/Sponsor representative has the right to urgently request additional information from the Investigator about such SAEs for reporting to the regulatory authorities.

In the context of reporting of SAEs, the trial period is defined as the period from the first administration of the investigational product to the end of the follow-up period.

During the trial period, the investigator is obligated to provide patients with necessary medical services.

If, prior to completion of the trial, patients develop an AE that results in exclusion from the trial, it is the responsibility of the investigator to ensure follow-up of that patient. Follow-up of the patient to ensure patient safety should take precedence over establishing the cause(s) for the development of the AE. The frequency of examinations during the follow-up period is determined by the investigator. All AEs/SAEs should be monitored until they are resolved or stabilized.

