9.4. Dealing with dropped out, excluded patients and missing data

No missing data will be completed, missing data will not be taken into account when performing statistical analyses.

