9.6. Population to be analysed

The following population groups will be used for the analyses:

1. The ITT (Intent-to-treat) population will include all randomized patients regardless of investigational product/placebo administration.
2. The mITT (modified Intent-to-treat) population will include patients who have completed the full course of therapy, regardless of the presence of Protocol violations/ deviations.
3. The PP (Per protocol) population will include patients who completed the trial in accordance with the Protocol.

At the stage of statistical data processing, additional analyses of the efficacy and/or safety of investigational product/placebo in subpopulations of patients of different age groups can be performed.

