13.4. Data collection

The data obtained during the trial are recorded in the eCRF.

Completion of the CRF must be done within the timeframe agreed upon with the Sponsor.

If a patient drops out of the trial early, the eCRF is completed up to the time of dropout, stating the reason for early completion of trial participation.

It is the responsibility of the Investigator to ensure that the data entered into the eCRF are complete and correct. The data recorded in the eCRF should be appropriately supported by source documentation.

It is the The Clinical Research Associate's responsibility to verify the information entered into the eCRF for compliance with the source documentation. The Investigator is required to provide source documentation to the Clinical Research Associate for data reconciliation.

If any discrepancies in the data are identified, the Clinical Research Associate should inform the Investigator. The Clinical Research Associate is not authorized to make corrections to the eCRF.

Corrections to the eCRF shall be made by the Investigator or a member of the trial team authorized to record data in the CRF in accordance with the relevant instructions.

13.5.Data transmission and processing

Once data entry is complete, a check will be performed to verify the validity, consistency and completeness of the data.

All missing data and discrepancies will be submitted to the investigational site as queries and clarified by the responsible Investigator. If no further adjustments to the base are needed, it will be declared closed and used for statistical analyses.

Data management activities will be conducted in accordance with the Sponsor's / CRO's current standard operating procedures (SOPs).

13.6.Storage and archiving of documents

By signing this Protocol, the Investigator agrees to comply with the procedures for retention and archiving of trial documentation. Source documentation and the Investigator Site File, including the participant identification sheet and trial-related correspondence, shall be retained. Key clinical trial documents should be kept at the investigational site. Clinical Trial documents may be destroyed only with the written permission of the Sponsor.

The Sponsor is responsible for archiving the Trial Master File.

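### Patients removed under section 5.3 leave follow-up as well as drug, so the planned ITT analyses have no scheduled Day 71 mRS for them

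*Protocol*

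**What the plan says.** **Removal.** Protocol 5.3 lists recurrent stroke, SAEs or AEs judged dangerous, any condition the investigator thinks requires withdrawal, late positive serology, a positive SARS-CoV-2 test, and "Need for additional therapy not permitted under this protocol". Section 4.5 treats meeting a criterion as grounds for ending participation. Section 11.8 counts keeping such a patient in as a significant deviation. Section 8.3.1 lists withdrawal of the product among actions for an AE, but 8.3.2 tells the investigator to "assess whether the patient can continue to participate in the trial (continue the IP or exclude the patient from the trial").

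**What is collected afterwards.** mRS is scheduled at Visits 0, 2 and 4 only (6.3.11). For leavers, 6.1 and 6.2 say "In case of early withdrawal of a patient from the trial, a Visit to End Patient Participation in the Trial is performed", with the Visit 4 activities and no day or window. Section 5.4.4 asks the investigator to arrange that visit when "the patient is withdrawn from the trial for any reason unrelated to the development of an AE". For AE withdrawals it mentions only AE monitoring. For a patient who received no dose it says "he/she is not followed up further". Section 13.4 adds: "If a patient drops out of the trial early, the eCRF is completed up to the time of dropout".

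**What is analysed.** The primary endpoint is mRS change at Day 71 (9.7.2). The per-protocol (PP) population is primary, and ITT and mITT are additional (9.7.2; SAP section 11). ITT "will include all randomized patients regardless of investigational product/placebo administration" (9.6). Under 9.4, "missing data will not be taken into account when performing statistical analyses"; SAP section 11 likewise supplies no missing values.

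**The concern.** The plan promises an efficacy analysis of all randomised patients but schedules no endpoint for those it removes. Some removal reasons, such as recurrent stroke or a serious adverse event, go with a poor mRS. If such removals differ between arms, a complete-case ITT comparison is biased, and no later analysis can recover scores that were never collected.

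This matters more because PP is primary. PP drops these patients by definition, so ITT is the planned analysis that could show whether removals drive the result. As written, it loses the same patients' Day 71 outcomes.

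**Working it through.** **1. The plan's own figures.** From protocol 9.1: effect 0.292, boundary 0.027, SD 0.802, one-sided α 0.05, power 80%.

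n per arm = 2 × (1.6449 + 0.8416)² × 0.802² / (0.292 − 0.027)² = 113.25, rounded up to 114. Total 228, and 228 / 0.75 = 304. These reproduce. The 25% allowance (76 patients) is for loss from PP. It is not an estimate of missing Day 71 mRS, because some non-PP patients still reach Visit 4.

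**2. Is a Day 71 mRS scheduled for anyone who leaves?**

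| Patient | mRS after baseline | Scheduled Day 71 mRS |
|---|---|---|
| Dosed, non-AE withdrawal | Visit 2 if reached; exit visit on an arranged date | No |
| Dosed, AE/SAE withdrawal | Visit 2 if reached; exit visit under 6.1/6.2, not mentioned in 5.4.4 | No |
| Randomised, never dosed | No follow-up under 5.4.4, though in ITT | No |
| Dies before Visit 4 | Appendix 2 has a death category (6), but no rule assigns it | No |

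**3. How many patients.** EPICA randomised 150 (2.3.2); 9 dropped out early, and Table 9.1 has 144 with an mRS change.

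- (150 − 144) / 150 = 4%; × 304 ≈ 12
- 9 / 150 = 6%; × 304 ≈ 18

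**4. Bias in the ITT difference.** Let an arm have removal fraction d, and let removed patients improve less than the others by g points. The observed mean is then the all-randomised mean plus d × g. With the same g in both arms:

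bias = (d on drug − d on placebo) × g

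More removals on drug flatter the drug; more on placebo work against it. Both inputs are assumptions.

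| Imbalance | Gap g | Bias (points) | Share of 0.292 |
|---|---|---|---|
| 1 percentage point | 1 | 0.01 | 3% |
| 2 percentage points | 2 | 0.04 | 14% |
| 5 percentage points | 3 | 0.15 | 51% |

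At 6% overall and 152 per arm, 2 percentage points means 7% v 5%, or 10.6 v 7.6 patients. Five means 8.5% v 3.5%, or 12.9 v 5.3.

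**5. Anchoring the gap.** A patient back at baseline disability has change 0, against EPICA means of 1.986 (placebo) and 2.278 (drug), so g is 2.0–2.3. A death scored 6 has change −1 from baseline 5 and −3 from baseline 3. The gap then runs from 1.986 + 1 = 2.99 to 2.278 + 3 = 5.28. Removals for late serology or a virus test would have g near 0.

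**6. Equal removal is not harmless either.** With 6% removed in each arm and no drug effect in them, the all-randomised difference is 0.94 × 0.292 = 0.274, while the observed one stays at 0.292.

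**The case against.** The strongest reply is that PP decides superiority, so nothing here changes the primary conclusion. That is right. The gap affects the additional ITT analyses. It may also touch the interim look, which 9.1 and 9.9 place on all 304 randomised patients without reconciling this with PP.

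Second, an mRS usually will exist: 6.1 and 6.2 require the exit visit for all early withdrawals, and the endpoint list says end of therapy without naming a day. On that reading only an analysis rule is missing. EPICA lends some support: 144 patients have a change score although 141 completed, so at least 3 non-completers contributed one, by a route the documents do not state. But the statistics sections define the endpoint at Day 71. An exit score counted as end of therapy would mix assessment days in a condition where patients improved by about 2 points over the course. A rule alone would not supply the endpoint.

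Third, the size is modest and assumed. The middle-case bias of 0.04 is under half the ITT standard error, 0.802 × √(2/152) = 0.092. The 51% figure needs about 13 v 5 removals, a split that has about 10% probability in either direction if removal is equal (exact binomial, 18 removals), plus an average gap worse than full return to baseline. EPICA reported no deaths. These points stand, and 51% should be read as an extreme.

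Fourth, AE/SAE cases are followed to resolution or stabilisation, and extra visits are allowed. Neither schedules an mRS.

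**Conclusion.** The point stands and should be fixed. Followed as written, the plan leaves the ITT analyses of mRS change and of the end-of-therapy mRS proportions without a scheduled Day 71 value for removed patients, some of them removed for prognostic reasons.

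The size rests on EPICA's 4–6% as a proxy for missing endpoints; the documents do not break those losses down by reason or explain the 6 absent from Table 9.1. Imbalance and gap are assumed. A plausible middle value is 0.04 points: small beside sampling error, but larger than the superiority boundary of 0.027. The PP result and the 114/228/304 sample size are untouched. What is at stake is how far ITT can serve as a check on PP.

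**What to change.** - In 5.3 and 5.4, separate stopping trial drug from refusing further follow-up. The rules on who stops drug stay as they are.
- Keep the exit visit for all withdrawals, AE withdrawals included, and bring 5.4.4 and 13.4 into line with 6.1 and 6.2.
- For every randomised patient who has not refused contact, dosed or not, record a dated mRS and vital status at Day 71(+2), by telephone or through a carer if needed. Score death as 6, as in Appendix 2.
- Label exit scores separately from Visit 4 scores, and use the Day 71 values in the ITT analysis.

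The cost is a protocol amendment, with the approvals that 11.7 requires, and one contact for each stopped patient, about 12–18 in total. Telephone calls are already in the design, so no new staff are needed, but the present calls do not include mRS, so sites need instructions for it. Telephone mRS may be less precise than a score taken in person, and patients who withdraw consent or cannot be reached remain missing.

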6.2. Description of visits

Period of screening, randomization and initiation of therapy

The duration of the screening period is no more than 1 day (24 hours). Visit 0 procedures can be performed on the same day as Visit 1 procedures.

Screening (Visit 0)

The patient being treated in the inpatient department of the neurology department of the investigational site is provided with information about the investigational product and the specifics of the trial in an accessible form. The patient is assured that qualified medical care will be provided if necessary, both during and after the trial, and that information about him/her obtained during the trial will be confidential. The patient must sign the Informed Consent Form in duplicate with his/her own hand (or with the participation of a legal representative if the patient is not physically able to sign). Sufficient time should be allowed to familiarise with the text of the Patient Information Sheet with the Informed Consent Form. One copy of the Informed Consent Form is given to the patient. Together with the Patient Information Sheet with the Informed Consent Form, the patient is given a life and health insurance policy for the patient taking part in a clinical trial of a medicinal product. The procedure for signing informed consent is described in more detail in Section 6.3.1 of this Protocol.

- After signing the informed consent, all patients undergo anthropometric measurements (height, body weight, BMI - the ratio of body weight in kg to height in m^2), followed by examination, including physical examination, neurological examination, measurement of blood pressure (BP), heart rate (HR), respiratory rate (RR), body temperature, electrocardiography (ECG), clinical and biochemical blood tests, urinalysis, blood tests to exclude hepatitis B and C, HIV infection, syphilis (results of serological tests obtained within 48 hours prior to screening can be used), rapid test for IgM antibodies to SARS-CoV-2 virus.

All patients with preserved reproductive potential should have a negative pregnancy test result. It is planned to use CT/MRI data performed within 48 hours prior to inclusion of the patient in the trial to confirm the underlying diagnosis. The patient is assessed using questionnaires (mRS, NIHSS). The investigator collects information about the patient's medical history, previous and current therapy, and assesses the patient's eligibility. If data are available for a patient from instrumental examinations performed within 48 hours prior to inclusion in the trial, they can be used to assess the patient's condition and eligibility for inclusion/non-inclusion. The use of such data shall be permitted only if the data are available in full and for all parameters required by the Protocol. The results of the examination are recorded in the patients' CRF. Based on the results of the examinations, the investigator makes a conclusion, based on which the patient is allowed or not allowed to participate further in the trial (Visit 1).

Thus, the following procedures are provided at this stage:

- Signing an informed consent form;
- Collection of demographic and anthropometric data, anamnesis;
- Physical examination
- Neurological examination;
- Assessment of vital signs (BP, HR, RR, body temperature);
- Clinical blood test;
- Blood chemistry;
- Blood tests for HIV, Syphilis, Hepatitis B and C (results obtained within 48 hours prior to Screening can be used);
- Urinalysis;
- Pregnancy test for women with preserved reproductive potential;

- ECG¹;
- Completion of specialized scales (mRS, NIHSS);
- CT/MRI²;
- Assessment of prior and concomitant therapy;
- Assessment of inclusion/non-inclusion criteria

Randomization and initiation of therapy

Visit 1

Randomization is performed for patients who meet inclusion criteria and do not have non-inclusion criteria. In the subpopulation of patients involved in the evaluation of the pharmacodynamic effects of the investigational therapy, blood samples are collected for the trial of pharmacodynamic effects. According to the randomization number, the patient is assigned to the investigational therapy. The prescribed therapy is started.

Thus, if the patient fulfils the eligibility criteria, the following procedures are carried out:

- Randomization
- Completion of specialised scales and calculation of indices (HADS, MoCA, Rivermead mobility index);
- Administration and initiation of the investigational therapy
- AE registration

Therapy period

Visit 2 (day 11/12³ from the start of therapy, Visit procedures are performed at the end of parenteral therapy)

The visit is conducted in the inpatient setting of the investigational site and includes the following procedures:

- physical examination,
- neurological examination,
- assessment of vital signs (BP, HR, respiratory rate, body temperature),
- evaluation of concomitant therapy,
- AEs registration;
- evaluation of exclusion criteria;
- clinical blood test,
- blood chemistry;
- urinalysis;
- ECG
- completion of specialised scales and calculation of indices (mRS, NIHSS, HADS, MoCA, Rivermead mobility index),
- dispensing of oral medication

The investigator decides on the patient's discharge from the hospital, instructs the patient on the rules of the trial, administration of the investigational therapy and planned Visits/procedures.

Telephone visit 1 (Day 24±2 from initiation of therapy; Day 14±2 from initiation of oral therapy).

¹ If data are available for a patient from instrumental examinations performed within 48 hours prior to inclusion in the trial, they can be used to assess the patient's condition and eligibility for inclusion/non-inclusion. The use of such data shall be permitted only if the data are available in full and for all parameters required by the Protocol.

² The plan is to use data from neuroimaging examinations performed within 48 hours prior to patient inclusion in the trial to assess patient status and eligibility for inclusion/non-inclusion. A repeat CT/MRI scan is not required if these findings are present.

³ If the first administration of the investigational product (start of parenteral therapy) falls on the second half of the day (first day of therapy - one administration), Visit 2 is performed on day 12 in the morning.

The investigator should contact the patient by telephone to assess concomitant therapy, to record AE and assess exclusion criteria, and to assess compliance.

Visit 3 (Day 40 (+2) from initiation of therapy; Day 30 (+2) from initiation of oral therapy):

The visit is conducted in the context of the patient's outpatient visit to the investigational site and includes the following procedures:

- physical examination,
- assessment of vital signs (BP, HR, respiratory rate, body temperature),
- evaluation of concomitant therapy,
- AEs registration;
- evaluation of exclusion criteria;
- dispensing/accounting for oral medication,
- compliance assessment

Telephone visit 2 (Day 55±2 from initiation of therapy; Day 45±2 from initiation of oral therapy):

The investigator should contact the patient by telephone to assess concomitant therapy, to record AE and assess exclusion criteria, and to assess compliance.

Visit 4 (day 71(+2) from start of therapy; end of therapy)

The visit is conducted in the context of the patient's outpatient visit to the investigational site and includes the following procedures:

- physical examination,
- neurological examination,
- assessment of vital signs (BP, HR, respiratory rate, body temperature),
- evaluation of concomitant therapy,
- AEs registration;
- evaluation of exclusion criteria;
- clinical blood test,
- blood chemistry;
- urinalysis;
- pregnancy test for women with preserved reproductive potential,
- ECG
- completion of specialised scales and calculation of indices (mRS, NIHSS, HADS, MoCA, Rivermead mobility index),
- IP take-back and compliance assessment

Additional in-person/out-person (phone calls) visits may be conducted if necessary in the reasonable judgement of the investigator, particularly to monitor the progression of SAEs. The scope of activities and procedures performed at additional visits will be determined by the investigator on an individual basis, depending on the indications.

In case of early withdrawal of a patient from the trial, a Visit to End Patient Participation in the Trial is performed, including activities identical to those of Visit 4.

